All participant data will be treated as confidential. Records will be safeguarded according to the policies of the University of Connecticut and Connecticut law. Participants will be assigned a three-digit identification code that reflects the number of participants in the study. Only these identification numbers will appear on the data collection documents. A master key matching participant names to identification numbers will be maintained in a locked secure location at UConn's Weight Management Research Group. The master key will be kept for 5 years after all data collection has ended. Only research staff will have access to the information or be able to associate identification codes with individuals. All raw data collected in paper form will be stored in locked filing cabinets. Electronic de-identified data will be retained in a database indefinitely. Audio recordings will be destroyed 5 years after data collection has ended. All data will be reported in aggregate form only, in order to protect individuals' identities. Individual participants will not be identified in any reports, papers, presentations or other media. During the consent process, participants will also be asked if they can be contacted for future studies. Under these circumstances, their name and contact information would be stored separately from all personal health information (e.g., weight, survey data, etc.) in a password protected computer, in a password protected file, on a secure server. Participants who agree to be contacted for future studies would be contacted and, at that time, decide whether they wish to learn more about the new study. The study's project coordinator will work closely with the PI and study personnel to ensure the secure storage of all project databases and questionnaires. If necessary, data will be transmitted to study staff using password protected and de-identified files.

Participants will complete screening and assessment surveys online. Online questions will be administered using Qualtrics, a well-established service that is committed to keeping all participant data secure and confidential. All data is stored in a password protected database at a web hosting site that provides top of the line virtual and physical security. The web hosting facilities make use of firewalls, real-time security alerting using intrusion detection scanners, and 24-hour monitoring from their network operations center. The website itself is safeguarded against common hacker tricks. Physical security of database servers includes perimeter fencing, green field space, card access, biometric entries, and mantraps, 24-hour security guards and continuous camera surveillance inside and outside the facility's buildings. To prevent the possibility that data will be intercepted as it travels the internet, all data is encrypted in transmission, both when survey participants fill out surveys and when survey creators download their data. All electronic files will be password protected to protect the information from unauthorized access.

Our mHealth app is housed at UNC and is password protected, with each participant using a unique username and password. Data are stored in a password protected database at a web hosting site that provides top of the line security. The web hosting facilities make use of firewalls, real-time security alerting using intrusion detection scanners, and 24-hour monitoring from their network operations center. The website itself is safeguarded against common hacker tricks. All downloaded electronic files will be saved on the secure UConn server, which is password protected to protect the information from unauthorized access. In the mHealth BE arm, participants will be asked to select pictures as "cues;" while research staff will not prompt participants to select pictures of themselves, it is conceivable that a participant may choose to do so (e.g., picture of previous thinner self). As noted in the consent form, participants are made aware of the privacy/confidentiality limitations of pictures and all web-based / text correspondence.

Informed Consent

Participants will be initially screened through a secure portal on our lab website; any screener items that require follow-up information will be obtained by calling the interested individual via phone. All data on the website will be encrypted and accessed only by project research staff. If an individual is interested in

participating, (s)he will be invited to a virtual orientation session via Zoom. In the event of a virtual orientation sessions, all orientation documents will be sent to interested individuals prior to the session (including the consent form) and they will be encouraged to review these documents before the virtual session. During this session, interested individuals will be provided with detailed information about the study's purpose, risks/benefits, design, and requirements by study staff and be given an opportunity to ask questions. These sessions are interactive in nature. Once all procedures are explained and questions are answered (which takes approximately 1 hour), participants will be allowed to leave the orientation meeting if they are no longer interested. If the individual remains interested in participating, (s)he will provide oral/virtual consent via the audio, chat, and video functions of Zoom. Study staff will record all consented participants; these data will be stored on the UConn research drive in a locked file. After consent is provided, the participant will be officially enrolled in the study.

Documentation of Consent:

For the virtual consent process, participants will be sent the adult consent form prior to their Zoom / virtual consent meeting. During the virtual consent / orientation session, they will be asked to provide consent via hand raise, oral indication, or by sending a message to study staff using the chat function in Zoom. Study staff will record who provides consent. This information will be saved in a password protected file on the UConn research drive.

References:

1. Kaiser. Distribution of the total population by federal poverty level (above and below 200% FPL), 2017. [Cited 2017 December 14.] Available from: <https://www.kff.org/other/state-indicator/population-up-to-200-fpl/?currentTimeframe=0&selectedDistributions=under-200percent&sortModel=%7B%22colId%22:%22Location%22,%22sort%22:%22asc%22%7D>.

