Study Protocol

Title: Research Intervention to Support Health Eating and Exercise

NCT#: 04353258

Date: December 17, 2025

Clinical Trial/GCP Training

Is this a research study in which one or more human subjects are prospectively assigned¹ to one or more biomedical or behavioral interventions² (which may include placebo or other control) to evaluate the effects of those interventions on health-related biomedical or behavioral outcomes³ (i.e a clinical trial)? Indicate “yes,” “no,” or “N/A” in the space immediately below.

Yes.

Is the study fully or partially funded by the NIH? Indicate “yes,” “no,” or “N/A” in the space immediately below.

Yes.

Have the required key personnel completed Good Clinical Practice (GCP) Training? Indicate “yes,” “no,” or “N/A” in the space immediately below. (Note that IRB approval will not be given for NIH funded clinical trials until all required key personnel complete the GCP training.)

Yes.

For EACH Participant Population State the Number of Participants to be Enrolled and Screened and/or the number of participant records reviewed (including, HIPAA covered health records and FERPA covered school records), if applicable:

This study will include N=195 participants. Participants will be adults (ages 18-75) from all sex (male, female, non-binary) and racial/ethnic groups. They will also be from all education levels and have an income of <=300% of the federal poverty line or qualify for benefits (e.g., WIC, SNAP, etc.). Given that this is a weight loss study, participants will have a body mass index (BMI) in the overweight/obese range (25-55kg/m²). In order to meet our participant randomization goal, a total of 300 participants will need to be enrolled into the study / sign consent.

Justification of Sample Size:

The trial is powered for the primary aim: efficacy of BE mHealth vs. mHealth at month 12. We aim to detect a clinically meaningful difference of 2.5 kg between arms.[99] Based on previous trials with

¹The term “prospectively assigned” refers to a pre-defined process (e.g., randomization) specified in an approved protocol that stipulates the assignment of research subjects (individually or in clusters) to one or more arms (e.g., intervention, placebo, or other control) of a clinical trial.

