²An intervention is defined as a manipulation of the subject or subject’s environment for the purpose of modifying one or more health-related biomedical or behavioral processes and/or endpoints. Examples include: drugs/small molecules/compounds; biologics; devices; procedures (e.g., surgical techniques); delivery systems (e.g., telemedicine, face-to-face interviews); strategies to change health-related behavior (e.g., diet, cognitive/behavioral therapy, exercise, development of new habits); treatment strategies; prevention strategies; and, diagnostic strategies.

³ 3. Health-related biomedical or behavioral outcome is defined as the pre-specified goal(s) or condition(s) that reflect the effect of one or more interventions on human subjects’ biomedical or behavioral status or quality of life. Examples include: positive or negative changes to physiological or biological parameters (e.g., improvement of lung capacity, gene expression); positive or negative changes to psychological or neurodevelopmental parameters (e.g., mood management intervention for smokers; reading comprehension and /or information retention, behavioral intervention for psychiatric symptoms); positive or negative changes to disease processes; positive or negative changes to health-related behaviors; and, positive or negative changes to quality of life.

similar designs and our own trials, we expect a common within-group standard deviation of 5kg and a 20% attrition rate. [10-12] Hypothesis testing will be based on linear mixed effects models for longitudinal data, which increase power by fully exploiting the strong correlation in weight measures across time. Given these assumptions, if a total of N=160 participants (BE mHealth: N=80; mHealth: N=80) are enrolled, the trial will have 88% power to detect a statistically significant result. Accounting for attrition, 35 more participants will be added, so a total of 195 participants will be needed for this trial.

For EACH Participant Population Describe Screening Procedures, if applicable:

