Design overview. This study will examine the efficacy of a mHealth Behavioral Economics weight loss treatment for adults from economically disadvantaged backgrounds. Participants will be randomly assigned to either the Behavioral Economics mHealth intervention (BE mHealth) or mHealth only (no behavioral economics treatment components). Both interventions will: (a) include behavioral weight loss material tailored to this population, (b) be matched for interventionist contact, and (c) be 12 months in duration. The only difference between the two arms is the inclusion of behavioral economics strategies in BE mHealth. Specifically, BE mHealth will involve provision of reinforcers (small monetary reinforcers) and training in Episodic Future Thinking (see below for details). Assessments will occur at baseline, 2, 6, and 12 months (primary endpoint) and at the 18-month follow-up (C1-C3). The 18-month follow-up is included to explore whether participants continue to engage with the two interventions and the durability of treatment effects in the two arms. The primary outcome for which the trial is powered is weight change at month 12. Mediators (reinforcing value of food, delay discounting), moderators (e.g., stress, resilience, environment), and cost-effectiveness of the two interventions will also be explored. Visits (orientation / consent, assessments, and intervention) will be conducted via a video conferencing platform like Zoom.

Randomization. Eligible participants will be randomized to either BE mHealth or mHealth. The statistician will conduct the randomization and will use a permuted block randomization scheme for each cohort. Given evidence of differential weight loss by racial / ethnic background and sex^[40, 64] randomization will be stratified on these variables. A 1:1 randomization scheme will be used.

Overview of the two interventions. The two interventions are matched on treatment modality, participant contact, treatment duration, and tailored weight loss content. That is, the only way in which BE mHealth and mHealth differ is in behavioral economics strategies. Please see table and details below.

Similarities between BE mHealth and mHealth. The two interventions will be matched on treatment modality (primarily mHealth), contact (a total of 16 sessions),

Similarities		
mHealth treatment platform	✓	✓
Tailored behavioral weight loss treatment materials	✓	✓
Up to 16 sessions	✓	✓
12-months of treatment	✓	✓
Differences		

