Limits of Assumptions. It is possible that baseline differences between groups, excessive study dropouts, and/or missing data by the interim measurement time points will limit the value of data analysis of measurements at the post-treatment time point. Baseline differences will be evaluated after the first measurement time point and effects on the power to detect differences in the primary outcome will be examined and communicated to the PI, safety monitor, and NIDDK. Given the monitoring plans outlined elsewhere in this document, and the fact that this is a randomized trial, it is exceedingly unlikely that there will be baseline differences between groups of any magnitude to threaten the validity of the study.

Our retention rates have been historically excellent (e.g., >90%), however, excessive drop-outs could occur. In the grant proposal, we allowed for 20% dropout in the recruited numbers. With 20% dropout rate in all groups and 5% Type I error, the primary hypothesis is testable at 88% power. Dropout rates higher than 20% would be of concern, so we propose to monitor the dropout rate quarterly. Alert points are set at dropout rates of 20% (low alert), 30% (mid-alert), 35% (high alert), and 40% (extreme alert). With early alerts to problems, action would be taken to avoid higher level alerts; if a higher level alert should arise, more drastic remedial action would be invoked. To elucidate the implications arising when dropout rates reach various alerts, the following table estimates the power of the study for the primary hypotheses as the dropout rate increases above 20% (at which the study power is 88% for the primary hypothesis).

Dropout rate	20%	30%	35%	40%
Alert level	low	mid	high	extreme
Power available	88%	82%	76%	70%

The actions taken at each level of alert are given below:

- Mid-level alert = Conference call between study investigators to discuss approaches to minimize further losses to follow-up/dropouts.
- High-level alert = Conference call between investigators to determine further alterations of study protocol to complete the study with no further losses
- Extreme-level alert = In the unlikely event of a 40% dropout rate, study investigators would convene on a conference call to discuss the usefulness of continuing the study.

Participant Confidentiality:

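### The 195 to be randomised does not keep 160 participants at the stated 20% attrition: it leaves 156 and covers 17.9%, at a cost of under one point of power

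*Combined protocol and SAP*

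**What the plan says.** The protocol's Justification of Sample Size sets the target effect: "We aim to detect a clinically meaningful difference of 2.5 kg between arms". It then gives the planning assumptions, "we expect a common within-group standard deviation of 5kg and a 20% attrition rate", and the resulting size: "if a total of N=160 participants (BE mHealth: N=80; mHealth: N=80) are enrolled, the trial will have 88% power". The last step is the attrition allowance: "Accounting for attrition, 35 more participants will be added, so a total of 195 participants will be needed for this trial". The paragraph on numbers to be enrolled adopts the same total: "This study will include N=195 participants". The Randomization paragraph fixes equal allocation: "A 1:1 randomization scheme will be used".

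Under Stopping Rules, the Limits of Assumptions paragraph returns to these figures. It says "In the grant proposal, we allowed for 20% dropout in the recruited numbers" and then "With 20% dropout rate in all groups and 5% Type I error, the primary hypothesis is testable at 88% power". The dropout alert table in the same section repeats 88% in its 20% column.

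The documents do not say how the 35 was derived, whether the 5% is one-sided or two-sided, or what correlation between repeated weights was assumed.

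**The concern.** Three figures are offered as consistent: 160 participants for 88% power, 20% attrition, and 195 randomised. If 160 must remain after a 20% loss, the total should be 160 divided by 0.80, and that is not 195. The Limits of Assumptions paragraph then relies on the same 20% and 88% as the reference point for quarterly dropout monitoring, where 20% is the first alert level.

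What is at stake is whether the stated N delivers the number of participants on which the stated power was computed. This paragraph is the protocol's only derivation of its sample size, so anyone who checks it will find the gap.

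**Working it through.** **Inputs.** Difference 2.5 kg, SD 5 kg, attrition 20%, 80 per arm and 35 added, all from Justification of Sample Size. Type I error 5% from Limits of Assumptions. Allocation 1:1 from Randomization. Two-sided testing is my assumption.

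**Step 1: reproduce the plan's 88%.** For two equal arms of size n, the non-centrality is 2.5 / (5 × √(2/n)).

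- At n = 80 it is 0.5 / √0.025 = 3.162. The normal approximation, Φ(3.162 − 1.960), gives 88.5%. The non-central t on 158 degrees of freedom gives 88.2%.
- One-sided testing at n = 80 would give 93.5%, which does not match, so the two-sided assumption fits the plan.

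The stated 88% is therefore the power of a plain two-sample comparison with 160 people who have month-12 data, with no credit for repeated measures. If the 160 were instead a number before attrition, 128 would remain (64 per arm) and the same formulas would give 80.1% to 80.7%. That does not match 88%, and it would leave no reason to add 35 for attrition. So 160 is the number meant to remain.

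**Step 2: the attrition step.**

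| Calculation | Result |
|---|---|
| Randomised to keep 160 after 20% loss: 160 / 0.80 | 200 |
| Adding 20% of 160 instead: 160 × 1.20 | 192 |
| Remaining from 195 after 20% loss: 195 × 0.80 | 156 (78 per arm) |
| Attrition at which 195 keeps 160: 35 / 195 | 17.9% |
| 35 as a share of 160: 35 / 160 | 21.9% |

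Neither usual way of allowing for 20% gives 195. The shortfall against 200 is 5 randomised, or 160 − 156 = 4 participants with month-12 data (4/160 = 2.5%).

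**Step 3: the effect on power.** At n = 78 the non-centrality is 0.5 / √(2/78) = 3.122.

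| With month-12 data | Normal approximation | Non-central t |
|---|---|---|
| 160 (80 per arm) | 88.5% | 88.2% |
| 156 (78 per arm) | 87.7% | 87.3% |
| Difference | 0.8 points | 0.8 points (before rounding) |

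The normal-approximation figure at 156 still rounds to the stated 88%; the non-central t figure rounds to 87%.

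**The case against.** The strongest reply is that the power check counts only people with month-12 data, while the protocol plans something else. Justification of Sample Size and Data Analysis specify linear mixed models fitted by restricted maximum likelihood, with weights at 2 and 6 months as well as 12. Someone who leaves after month 2 or 6 still contributes information, and the 88% takes no credit for it.

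An illustration shows the scale. It assumes data missing at random, 156 participants with month-12 data, 39 dropouts, and a single earlier weight change whose correlation with the month-12 change is r (a figure the documents do not give). Matching the information from 160 then needs:

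- r = 0.35 if every dropout has that earlier weight;
- r = 0.47 if half do;
- r = 0.65 if a quarter do.

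With no post-baseline weights from dropouts there is no gain. This reply stands as far as power is concerned: 195 could deliver 88% at 20% attrition. It does not change the head count, which is still 156 and not 160.

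A second reply is that 195 lies between 192 and 200 and may be a deliberate approximation. That is possible. The documents do not explain the 35, so they do not show how the discrepancy arose, only that the three figures do not agree.

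A third reply is that the protocol reports past retention above 90%. At 90%, 195 × 0.90 = 175.5, well over 160. This reduces the practical importance, but the plan states its power at 20% and its N should be described on that basis.

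A reader might also infer that the trial is underpowered, or that its 88% is wrong. The documents support neither, since the difference is under one point and depends on the formula used. Nor is the chance of ending below 160 a useful measure. With independent dropout at 20% it is about 73% for 195, but about 46% even for 200, because a size set to the expected number often falls just short of it.

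**Conclusion.** The point holds as a small inconsistency in the sample-size derivation. On the plan's own inputs, 195 randomised keeps 160 only up to 17.9% attrition; at the stated 20% it keeps 156, 4 fewer than the number that reproduces 88% power. The statement that 20% dropout was allowed for in the recruited numbers is therefore not exact.

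The head count rests on the plan's figures alone. The power figures (87.3% to 87.7%, against 88.2% to 88.5%) assume a two-sided 5% test, a 2.5 kg difference, an SD of 5 kg and a two-sample comparison at month 12 without any mixed-model gain. That gain is not quantified in the documents and could offset the difference in part or in full. The stated 88% is not shown to be materially wrong, and nothing here calls the design into question.

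**What to change.** Keep N = 195 and restate what it provides in Justification of Sample Size, for example:

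> With 195 randomised, 160 participants will have month-12 data (88% power) provided attrition does not exceed 17.9%. At 20% attrition 156 remain, and power is about 87% to 88% before any gain from the mixed model.

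Bring the two sentences on the 20% dropout allowance in Limits of Assumptions, and the 20% column of the alert table, into line with this. It would help to add how the 35 was chosen and that the 5% is two-sided, if it is.

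The cost is a few sentences of wording and a slightly less favourable description of the allowance. Enrolment, the analysis and the dropout alert thresholds do not need to change.

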
Anticipated Study Time Frame:

Participants will be recruited in 4 Cohorts. Recruitment and screening for Cohort 1 is anticipated to begin in the summer of 2021. All intervention and assessment visits will be completed by Year 6 (no cost extension year; COVID delays), Quarter 3. The last quarter of Year 6 will be reserved for data analysis, manuscript preparation, and dissemination of study findings. An updated, detailed timeline is presented below (Q=Quarter; C=Cohort).

	Year 1				Year 2				Year 3				Year 4				Year 5				Year 6				
	Q1	Q2	Q3	Q4																					
Start-up	X	X	X	X	X	X	X	X																	
C1 recruitment								X																	
C1 measurement								X	X	X	X	X	X	X	X										
C1 treatment								X	X	X	X	X	X	X	X										
C2 recruitment									X																
C2 measurement									X	X	X	X	X	X	X	X									
C2 treatment									X	X	X	X	X	X	X	X									
C3 recruitment										X															
C3 measurement										X	X	X	X	X	X	X	X	X	X	X					
C3 treatment										X	X	X	X	X	X	X	X	X	X	X					
C4 recruitment																X									
C4 measurement																X	X	X	X	X	X	X	X	X	
C4 treatment																X	X	X	X	X	X	X	X	X	
Data analyses & dissemination																									X

Design, Procedures, Materials and Methods:

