The primary outcome for which the trial is powered is weight change from baseline to month 12. Differences in baseline characteristics in BE mHealth vs. mHealth participants will be examined using either t-test, Chi-Square tests or analysis of variance when appropriate. If baseline differences exist, they will be controlled for in outcome analyses. Distributional properties of continuously scaled variables will be examined to determine if normalizing transformations should be applied or if distributions other than normal should be used in the models. Pairwise contrasts among study groups using linear mixed effects models will be fitted by restricted maximum likelihood using REML as implemented in the PROC MIXED procedure or PROC GLIMMIX SAS 9.3 if residuals do not meet normality. Unconditional models will be fitted to assess for variability in participant intercepts and slopes, and determine whether these factors should be treated as random effects in conditional models. Unconditional models will also be used to evaluate whether the trajectory of the outcome is best characterized as linear / non-linear (quadratic and cubic). Estimated mean differences will be developed using linear contrasts and assessed with Wald statistics. These analyses will result in a detailed model of weight change across the 12-month trial. Within the linear mixed effects model, an a priori test of the difference between least squared means for treatment arms at the 12-month time point, adjusted for covariates, will test for between-arm differences at the 12-month assessment.

Missing data. Although concerted effort will be made to minimize missing data, we anticipate missing data due to refuted responses or lost to follow-up. Type of missingness will be evaluated and missing values will be imputed using full information or restricted maximum likelihood estimation^[100] depending on type of missing data, completely at random or just random missing data. All variables in our models will be used to impute missing data. Sensitivity analyses will be used to compare results with and without imputed values.

Inclusion/Exclusion Criteria:

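### The month-12 primary test names no covariates, and its only stated selection rule will almost never pick the stratification factors, sex and race/ethnicity

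*Combined protocol and SAP*

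**What the plan says.** The Data Analysis section of the combined protocol and SAP makes the primary test an a priori comparison, within a linear mixed model, of "least squared means for treatment arms at the 12-month time point, adjusted for covariates". It lists no covariates. Earlier in the same section, baseline characteristics are to be compared between arms by t-test, chi-square or analysis of variance, followed by: "If baseline differences exist, they will be controlled for in outcome analyses". No threshold is given.

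Baseline weight is only partly specified. The outcome is change from baseline to month 12, and "Unconditional models will be fitted to assess for variability in participant intercepts and slopes". The text does not say whether baseline weight is a change-score reference, a covariate or one of the repeated outcomes.

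The Randomization paragraph stratifies on two variables, "Given evidence of differential weight loss by racial / ethnic background and sex", and the statistician "will use a permuted block randomization scheme for each cohort". The time frame section adds: "Participants will be recruited in 4 Cohorts".

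Under Stopping Rules, Limits of Assumptions: "Baseline differences will be evaluated after the first measurement time point". The same paragraph holds that, in a randomized trial, "it is exceedingly unlikely that there will be baseline differences between groups of any magnitude to threaten the validity of the study".

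**The concern.** The rule selects covariates by chance imbalance, not by how well they predict weight change. Stratified permuted blocks remove nearly all chance imbalance in sex and race/ethnicity. These are the two variables the plan itself regards as related to weight loss, and they are the ones the rule is least likely to select. The rule works only on unstratified variables, where a flagged difference is luck.

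Two things are at stake. First, the primary model is not reproducible from the text: two statisticians could follow it and fit different covariate sets. Second, if the stratification factors do predict weight change, leaving them out after balancing on them gives a standard error that is somewhat too large and forgoes some precision.

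**Working it through.** **1. The plan's own power figure.** Inputs from the sample-size section: difference 2.5 kg, SD 5 kg, 80 per arm. The 5% type I error comes from Limits of Assumptions; two-sided is assumed. The normal formula gives 88.5% and the noncentral t gives 88.2%, so the stated 88% reproduces. With 195 randomised and 20% attrition, 195 × 0.8 = 156, or 78 per arm, and power is 87.7%.

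**2. How often the rule selects the stratification factors.** Simulated trials (2,000 per stratified scenario): 195 participants, 4 cohorts, 1:1 permuted blocks within cohort × sex × race/ethnicity, and an uncorrected chi-square test at 0.05. Block size, category shares and threshold are not in the documents, so they were varied or assumed.

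| Setting | Sex flagged | Race/ethnicity flagged | Either |
|---|---|---|---|
| Stratified; blocks of 2-8; sex 80/20, 90/10 or 80/18/2; race/ethnicity 50/50 or 45/30/20/5 | 0-1.7% | 0-0.15% | 0-1.8% |
| Simple randomization, for comparison | 5.6% | 4.5% | 9.7% |

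If race/ethnicity is stratified in 2 groups but tested in 5, it is flagged in about 2.4% of trials.

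**3. How often the rule admits something by luck.** Take five unstratified variables: age, education, income, household size and baseline weight. The chance that at least one is flagged is 1 − 0.95⁵ = 23%. This assumes independence and a 0.05 threshold. The protocol itself links income and education, so 23% is only a rough guide.

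**4. Cost of omission, by formula.** Let R² be the share of month-12 weight-change variance explained by sex and race/ethnicity. The documents give no value, so a range is used. With 78 per arm and exact balance:

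- Reported SE without the factors: 5 × √(2/78) = 0.801.
- True SE, which is also the SE with the factors included: 0.801 × √(1 − R²).
- Type I error if omitted: 2 × [1 − Φ(1.96 × 0.801 / true SE)].
- Power if omitted: Φ((2.5 − 1.96 × 0.801) / true SE).
- Power if included: Φ(2.5 / true SE − 1.96).

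| R² | True SE | Reported SE too large by | Type I error, omitted | Power, omitted | Power, included |
|---|---|---|---|---|---|
| 0 | 0.801 | 0% | 5.0% | 87.7% | 87.7% |
| 5% | 0.780 | 2.6% | 4.4% | 88.4% | 89.3% |
| 10% | 0.760 | 5.4% | 3.9% | 89.0% | 90.8% |
| 15% | 0.738 | 8.5% | 3.4% | 89.6% | 92.3% |

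The gain from including the factors is therefore 0.9, 1.8 and 2.7 power points at R² of 5, 10 and 15%. To give R² a scale, assume 20% men and two equal race/ethnicity groups. A 2 kg difference by each factor gives (2² × 0.16 + 2² × 0.25)/25 = 6.6%, and 3 kg by each gives 14.8%.

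**5. Which terms are needed.** A four-visit mixed-model simulation used 20% dropout, unstructured covariance and assumed effects growing over time. It also carried cohort, with no effect.

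- *Baseline as a covariate, R² 15%:* the month-12 SE was 0.749 with no factors, 0.731 with main effects and 0.694 with factor-by-time terms. Main effects alone capture (0.749 − 0.731)/(0.749 − 0.694), about a third of the gain.
- *Baseline as a repeated outcome:* main effects gave nothing (0.744 with or without them), because they shift weight level and not weight change.
- *R² 0, baseline as a repeated outcome:* all terms together raised the SE from 0.744 to 0.747 (0.4%) and power fell from 91.2% to 90.2%.

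This simulation supports the choice of terms more than the exact size of the gain. It is not the random-intercept-and-slope model the plan describes. In its repeated-outcome version, the reported SE without the factors exceeded the empirical SD by only 0.8/2.9/4.1% at R² 5/10/15% (0.744 against 0.738/0.723/0.715), less than the formula gives.

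**The case against.** The strongest reply is that omission is inferred. The phrase about covariates and the baseline-difference rule are in separate sentences, and the plan does not say the rule is the sole source of covariates. A team that reads the stratification factors into that phrase loses nothing. This stands. What is established is that the covariates are unnamed and that the one stated rule would not bring these factors in.

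The second reply is that the gain is unproven. It depends on an R² the documents do not give: 0.9 power points by formula at 5%, and possibly a small loss at 0. This also stands, and it limits the point to an improvement of method.

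A reader might infer that covariates will be picked after looking at outcomes. The text does not support this. It places the comparison after the first measurement, so selection uses baseline data. With 4 cohorts, the pooled comparison is complete only once the last cohort is enrolled, but it remains a baseline comparison.

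**Conclusion.** The point holds as a specification gap with a modest statistical cost, and it should be fixed. The month-12 contrast has no named covariates. The only stated selection rule would pick sex or race/ethnicity in about 0-2% of trials. That result is stable across the block sizes and category mixes tried, but it assumes that differences are judged by a test at 0.05.

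If the factors are in fact left out and explain 5-15% of the variance, the formula puts the reported SE 2.6-8.5% too large, type I error at 4.4-3.4% in place of 5%, and the power forgone at 0.9-2.7 points. If they explain nothing, nothing is forgone.

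A reader might go further and conclude that the primary estimate is biased, that type I error is inflated or that the trial falls short of its stated power. None of these follows. Omission after stratification makes the test conservative. For R² of 5% or more, power with the factors omitted is still 88.4% or higher, against the stated 88%. At R² 0 it is 87.7% whether or not the factors are included, so omission is not the cause of that small difference.

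**What to change.** Replace the sentence that controls for observed baseline differences with wording such as:

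> The primary model includes sex and race/ethnicity, in the categories used for stratification (sparse categories combined by a rule fixed before any outcome is compared by arm), and baseline weight as a covariate, with post-baseline weight change as the outcome. Sex-by-time and race/ethnicity-by-time terms are included so that the factors can explain change at month 12. Baseline characteristics are tabulated descriptively. Adjustment for any other variable because it differs between arms is a sensitivity analysis.

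The reference to covariates in the month-12 contrast should then point to this list. Cohort may be added because blocks are run within it, but the documents give no evidence that it predicts weight change, so it need not be mandatory.

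The cost is SAP wording, a few degrees of freedom and, if the factors predict nothing, a very small loss of power: up to about 1 point in the simulation above, which also carried cohort terms. That cost was not tested with polynomial time trends. With baseline as a covariate, only months 2, 6 and 12 remain as outcomes in the 12-month model, so its mean trend can be at most quadratic and the cubic option falls away. No new data are needed: sex and race/ethnicity are already required for stratification, and baseline weight is already measured.
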